10.3. Contraindications to Vaccination

The following events constitute a temporary contraindication to study vaccination. If any of these events occur at the scheduled time for vaccination, the vaccination can be rescheduled (as long as this is in agreement with the allowed windows (see Section 9.1.2):

- Acute illness at the time of vaccination. This does not include minor illnesses, such as diarrhea or mild upper-respiratory tract infection.
- Fever (body temperature $\geq 38.0^{\circ}\text{C}$) at the planned time of vaccination.

If the vaccination visit cannot be rescheduled within the allowed window or the contraindications to vaccination persist, the HPX3002/HVTN 706 safety review team should be contacted for further guidance.

10.4. Withdrawal From the Use of Research Samples

Withdrawal From the Use of Samples in Future Research

The participant may withdraw consent for use of samples for research (refer to Section 16.2.5, Long-Term Retention of Samples for Additional Future Research). In such a case, samples will be destroyed after they are no longer needed for the clinical study. Details of the sample retention for research are presented in the ICF.

11. STATISTICAL METHODS

Statistical analysis will be done by the sponsor and its partners or under the authority of the sponsor. A general description of the statistical methods is outlined below. Specific details will be provided in the SAP.

11.1. Participant Information

For all participants, descriptive statistics of demographic (eg, sex assigned at birth, participant-identified gender at screening, age, height, weight, male circumcision, body mass index [BMI], and race) and other baseline characteristics (eg, medical history, including history and family history of immune disorders, concomitant diseases, Ad26 baseline serostatus) will be provided by vaccination group.

11.2. Analysis Populations

The following study populations or analysis sets are used for addressing the study objectives. This terminology is used throughout this protocol and SAP. The following sets and populations will include all vaccinated participants with respect to the vaccine actually administered.

1. Full Analysis Set (FAS): all randomized participants who receive at least one vaccine administration. This will be the primary population for the safety analysis.
2. Modified Intent-to-Treat (mITT) Population: participants in the FAS who are HIV-1 negative on the date of first vaccination.
3. Modified Intent-to-Treat-2 (mITT-2) Population: participants in the FAS who have a negative HIV test 4 weeks post 3rd vaccination visit (ie, at the Month 7 Visit).
4. Per-Protocol (PP) Population: participants in the FAS population who have a negative HIV test 4 weeks post 3rd vaccination visit (ie, at the Month 7 Visit), who received all planned vaccinations at the first three vaccination visits within the respective visit windows. This will be the primary population for the efficacy analysis.
5. Modified Intent-to-Treat-3 (mITT-3): participants in the FAS population who have a negative HIV test 4 weeks post 3rd vaccination visit (ie, at the Month 7 Visit), who received all planned

vaccinations at the first three vaccination visits, irrespective whether within or outside the respective visit windows. This will be an additional population for efficacy analysis, and potentially for immune correlates.

6. Full Immunization Set (FIS): participants in the FAS who are HIV-1 uninfected 4 weeks after the 4th vaccination visit (ie, at the Month 13 Visit) and who receive all planned vaccinations within the respective visit windows.
7. At risk Immunogenicity Cohort (IC-at risk): participants in the FAS who are selected for measurement of immune response endpoints at the primary immunogenicity timepoints and who are HIV-1 uninfected 4 weeks after the 3rd vaccination visit (ie, at the Month 7 Visit).

The analyses of safety will be performed on the FAS. The primary analysis of VE will be based on the PP population. Secondary analyses of VE will be based on the mITT, mITT-2, and mITT-3 population, and the FIS. For those with immunogenicity outcomes, analyses of vaccine immunogenicity and immune correlates may be based on PP, mITT-3, IC-at risk and the FIS. Other populations may be defined in the SAP for the purpose of exploratory (correlate) analyses.

11.3. Sample Size Determination

This study is designed to test the primary hypothesis of VE in the PP population:

$H_0: VE(7-x \text{ months}) \leq 20\%$ versus the $H_1: VE(7-x \text{ months}) > 20\%$, with $24 \leq x \leq 30$ (See Section 11.5.1.1).

If the lower bound of the 95% CI for $VE(7-x \text{ months})$ is $>20\%$ at the primary analysis, the corresponding H_0 will be rejected.

The sample size calculations are based on the power of a 1-sided 0.025-level Wald test for comparing cumulative incidences of HIV-1 infection by the Month x visit ($24 \leq x \leq 30$) between randomized groups, in the presence of the sequential monitoring of VE. Power is computed based on simulating 10,000 efficacy trials using the R package seqDesign^{14,24} under the following assumptions:

[figure not shown]
- 10% annual dropout incidence in both groups;
- 5% of participants with at least one missed vaccination (excluded from PP population);
- VE 20% in the first 7 months after first vaccination;
- VE 65% from Month 7 onwards;
- 12-month uniform accrual with halved accrual during the first 3 months;
- Visits approximately every 3 months for HIV-1 diagnostic tests;
- 2% annual HIV-1 incidence in the placebo group;

Under these assumptions, a study of 3,800 participants (randomized 1,900:1,900 to vaccine:placebo) is expected to yield a total of 78 HIV-1 infections in the PP population between

the Month 7 and Month 30 visits, considered to be the TNI needed to achieve approximately 90% power for rejecting the primary H0, under an alternative VE of 65% and with a one-sided error rate of 2.5%.

The timing of unblinding and conducting the primary analysis and the definition of the primary efficacy endpoint will be determined by when the TNI is reached within a given follow-up period x ($24 \leq x \leq 30$) for each participant. In practice, when the last participant has reached his/her Month 24 visit (or discontinued earlier), it will be assessed whether the TNI has been obtained within the period of Month 7-Month 24. If at that time the number of HIV-1 infections between Month 7 and Month 24 is greater than or equal to the TNI, the primary analysis may be conducted using VE(7-24 months) as the primary efficacy endpoint. Only if this primary H0 is rejected, VE(7-30 months) will be tested as secondary hypothesis, using a fixed sequence testing strategy, without adjustment for the Type-I error, and using all available durability data between Month 24 and Month 30. If the number of infections between Month 7 and Month 24 is less than the TNI, the study will continue for 3 months until the last participant has reached their Month 27 visit. The same procedure is repeated as described above, using all available HIV-1 infections between Month 7 and Month 27 and with VE(7-27 months) as the primary efficacy endpoint. If the number of infections between Month 7 and Month 27 is less than the TNI, the study will continue for 3 months until the last participant has reached his final study visit at Month 30. At that point, the primary analysis will be conducted regardless of whether the TNI has been reached, using VE(7-30 months) as only efficacy endpoint.

The statistical strategy is schematically presented in [Figure 1](#).

Figure 1: Primary Efficacy Testing – Schematic Overview

H0: null hypothesis; M: month; TNI: Target Number of Infections; VE: vaccine efficacy

Note that investigators and participants will remain blinded with regards to their treatment assignment, at least until the last participant has reached the Month 30 visit or discontinued earlier.

Both the study's sample size as well as the TNI may be adjusted during the study, but prior to unblinding, to ensure sufficient power at the time of the primary analysis. Whereas adjustment of the sample size may be based on internal (but sponsor-blinded) study data (through monitoring of the pooled HIV-1 incidence) as well as on external study data (eg, Phase 2b HPX2008/HVTN 705), any adjustment of the TNI will solely be driven by data external to this study (eg, Phase 2b HPX2008/HVTN 705). Full details on the possible sample-size reassessment will be described in the DSMB Charter and the SAP.

To cope with the dynamic environment of the development, approval and uptake of other prophylactic methods, such as PrEP (which would result in lower than expected annual incidence rates and thus lower study power), an estimated annual incidence rate in the control group of 2% was used to size this study.

[figure not shown]
Under the study assumptions as described above, the study will also have approximately 80% power for the secondary efficacy endpoint VE(0-x months), assessing VE in the mITT population and accounting for all HIV-1 infections starting from Month 0 (Day 1).

Rationale for the HIV-1 Incidence Assumptions

This study will recruit a large population of highest-risk MSM and transgender individuals who have sex with men from many regions. In 2011, 62% of estimated new HIV diagnoses in the United States were attributed to male-to-male sexual contact; 39% of these MSM were black or African American.⁹ Lifetime risk was 1 in 68 for males and 1 in 253 for females. Lifetime risk for men was 1 in 22 for blacks, 1 in 51 for Hispanic/Latinos, and 1 in 140 for whites. By risk group, the highest risk was among MSM (1 in 6) and the lowest was among male heterosexuals (1 in 524). Most of the states with the highest lifetime risk were in the South.¹⁹ Recent data from clinical studies show placebo incidence rates in high risk MSM of 6.6% in the Ipergay study (France, Canada)²⁸, 3.9% in the iPrEX study for high risk MSM (USA, Brazil, Peru, Ecuador, South Africa and Thailand)¹⁵, HVTN 505 yielded annual incidence rates of 2.3% in circumcised MSM and TG (USA)¹⁸. To help identify the study participants pre-trial assessments and data will be collected regarding incidence in potential sites.

The assumption of 2% annual HIV-1 incidence in the placebo group accommodates background PrEP use by assuming incidence is decreased by the person-years at risk during which PrEP is used, the efficacy of PrEP during PrEP use and the adherence to PrEP use. [Figure 2](#) shows the impact of assumed PrEP use and adherence on annual HIV-1 incidence in the placebo group when the initial incidence (in the absence of PrEP) is 3% or 4% and the efficacy of PrEP is assumed to be 90%.

Figure 2: Impact of Assumed PrEP use and Adherence on Annual HIV-1 Incidence in the Placebo Group

HIV-1: human immunodeficiency virus type 1; PrEP: pre-exposure prophylaxis

Based on the assumption of 3% annual incidence in the absence of PrEP and, about 35% of person-years at risk during PrEP use and 90% PrEP efficacy during use would provide us with the assumed 2% annual placebo incidence rate.

A total sample size of 3,800 participants, as based on the efficacy endpoints, will also provide enough power for assessing safety of the vaccine regimen. The probability of observing at least one adverse event occurring at a rate of 1/100 is >99.9% with approximately 1,900 vaccinees. The probability of observing at least 1 adverse event occurring at a rate of 1/1,000 is 85% with approximately 1,900 participants. If no events will be observed for a specific (serious) adverse event, then the Bayesian posterior probability that the adverse event rate is below 1/1,000 equals 95% for 1,900 participants and would provide us with 95% confidence that the true incidence is no more than 0.16%.

11.4. Study Monitoring

The study will be formally monitored. This may lead to a modification or termination of the study. The set of monitoring rules will include monitoring for potential harm, non-efficacy and operational futility. Monitoring rules applied in the current simulations are preliminary and subject to finetuning based on operating characteristics but will be formally finalized prior to study start and fully documented in the SAP and DSMB charter. The sequential monitoring to be applied to this study will follow the principles as discussed in Gilbert et al.¹⁴ Monitoring of the VE and underlying HIV-1 incidence will occur through the study's DSMB. A summary of the monitoring rules for vaccine efficacy, as used in the current simulations, is provided in Table 4 below.

Eventually, the monitoring rules as agreed with the independent DSMB and described in the DSMB charter will take priority over the ones presented below.

Table 4: Summary of interim monitoring of VE

Monitoring Outcome	Hypotheses	Testing Approach	Size	Monitoring Plan	Timing of analyses
Potential Harm	$H_0: VE(0-30) \geq 0\%$ vs. $H_1: VE(0-30) < 0\%$	Exact 1-sided binomial test of the proportion of infections assigned to the vaccine group	1-sided alpha=0.05	Near-constant 1-sided p-value cut-off controlling FWER at alpha=0.05	After every mITT infection starting at the 10 th total until the first non-efficacy analysis
Non-Efficacy	$H_0: VE(0-30) \geq 50\%$ vs. $H_1: VE(0-30) < 50\%$ and $H_0: VE(7-30) \geq 50\%$ vs. $H_1: VE(7-30) < 50\%$	Wald Test	1-sided alpha=0.025	Unadjusted 95% CIs for VE(0-30) and VE(7-30): lower bounds <0% and upper bounds <50%	6-monthly starting at 40 mITT infections and then through the primary analysis

CI: confidence interval; FWER: family-wise error rate; H_0 : null hypothesis; H_1 : alternative hypothesis; mITT: modified intent-to-treat; VE: vaccine efficacy; vs.: versus

11.5. Efficacy Analysis

The primary efficacy analysis will be performed when all participants have reached the Month x (with $24 \leq x \leq 30$) visit or discontinued earlier and the TNI has been reached in the study. Refer to [Figure 1](#) for more information on the timing and strategy of statistical testing.

11.5.1. Vaccine Efficacy Analysis

The primary analysis of VE will evaluate the number of HIV-1 infections in the vaccine group compared to the number of HIV-1 infections in the placebo group between Month 7 and Month x (with $24 \leq x \leq 30$) in the PP population. The H_0 of VE will be tested $VE(7-x \text{ months}) \leq 20\%$ versus the H_1 $VE(7-x \text{ months}) > 20\%$. Vaccine efficacy is defined as 1-cumulative incidence ratio (vaccine versus placebo) between Month 7 and Month x after first vaccination and is estimated by the transformation of the Nelson-Aalen estimator for the cumulative hazard function. If the lower bound of the 95% CI for $VE(7-x \text{ months})$ is $> 20\%$ (equivalently, the 1-sided p-value for testing $H_0: VE[7-x \text{ months}] \leq 20\%$ is below 0.025), the H_0 will be rejected in favor of the H_1 .

11.5.1.1. Primary Vaccine Efficacy Analysis: HIV-1 Infection

The primary analysis will be done in the PP population, where participants who become HIV-1 infected or who drop out before Month 7 or who have not received all of the first three vaccinations within the specified time window, will be excluded from the analysis. The date of HIV-1 diagnosis will be the draw date of the first sample that leads to a positive test result by the study protocol's diagnostic algorithm. Dropouts will be censored at the time of their last HIV-1 negative test. To evaluate the primary VE endpoint, the number of HIV-1 infections in the vaccine group will be compared to the number of HIV-1 infections in the placebo group between Month 7 and x months since the first vaccination (with $24 \leq x \leq 30$). The vaccine effect will be assessed using a ratio of

cumulative incidences of HIV-1 infection between Month 7 and x (vaccine versus placebo), estimated using the transformed Nelson-Aalen cumulative hazard function estimator and tested via a Wald test.

11.5.1.2. Secondary/Exploratory Vaccine Efficacy Analyses

As a key secondary objective, the VE beyond Month 7 will be evaluated in all participants, regardless of whether they received the first three vaccinations according to the protocol-specified schedule (mITT-2 population, see Section 11.2 for definition). Other secondary objectives will evaluate the VE over different time intervals (eg, VE[0-x months], VE[13-x months]) and in different populations (eg, mITT, mITT-2, mITT-3, FIS), using similar methods as described above. Cox proportional hazards model will also be used for estimating VE(7-x months), measured by one minus the hazard ratio (vaccine versus placebo) and for testing whether the VE(7-x months) differs from 20%.

To account for potentially confounding factors, subgroup and covariate-adjusted analyses will be performed. These subgroups/covariates will include PrEP use, baseline Ad26 seropositivity status and titers, presence of risk factors for HIV infection, and other baseline demographic factors. Efforts will be made to estimate vaccine efficacy in complete absence of PrEP use in a counterfactual framework.

In addition, an exploratory analysis that employs Bayesian methods will be conducted to evaluate VE.¹³ The prior to be used for this analysis will be a robust, meta-analytic one based on pre-specified weighting of the external Phase 2b data (study HPX2008/HVTN 705) as informative prior and a non-informative prior.³¹ Details of pre-specified weights and priors will be specified in the SAP.

If VE is established, an attempt will be made to identify correlates of increased risk of HIV-1 infection as well as correlates of VE, best individual-level classifiers of HIV infection and to assess mediators of vaccine efficacy. To this extent, appropriate statistical methodology will be applied or developed, and will be described in a (separate) SAP for correlate identification. If significant VE is observed, a pre-specified case-control study of immune responses elicited by vaccination in active vaccine recipients will be performed to identify vaccine-induced correlates of protection and/or risk. Both single parameter and combinations of multiple immunologic parameter models will be explored. The presence of time-dependent correlates of protection will be examined in addition to single time point immune responses, including the peak immune response after the primary vaccination series, or the time point most closely preceding the diagnosis of HIV-1 infection. To further ascribe immune correlates of protection and/or specifically of VE, placebo case and control samples will also be included in a secondary stage of analysis.

11.6. Safety Analysis

No formal statistical testing of safety data is planned. Safety data will be analyzed descriptively. All safety analyses will be tabulated by vaccination group (active vaccine, placebo) and based on the FAS.

Tabulations will be presented by time of occurrence relative to the preceding vaccination (7 days for solicited adverse events and 28 days for unsolicited adverse events, 6 months after last vaccination for AESIs).

Baseline for all safety parameters will be defined as the last evaluation done before the first dose of study vaccine.

11.6.1. Reactogenicity: Solicited Adverse Events

The number and percentage of participants experiencing each type of solicited adverse event will be tabulated by severity and vaccination group, and the percentages will be displayed graphically by group. For a given solicited adverse event, each participant's adverse event will be counted once under the maximum severity for each vaccination dose.

11.6.2. Unsolicited Adverse Events, AESIs, MAAEs and Serious Adverse Events

The verbatim terms used in the CRF by investigators to identify adverse events will be coded using the Medical Dictionary for Regulatory Activities (MedDRA). Tables will show, by vaccination group, the number and percentage of participants experiencing an adverse event within a system organ class or within a preferred term category by severity and by relationship to study vaccine. All reported adverse events and events-related diary information with onset or worsening within 28 days after each vaccination (ie, treatment-emergent adverse events) will be included in the analysis. For each adverse event, the percentage of participants who experience at least 1 occurrence of the given event will be summarized by vaccine group. A participant with multiple adverse events within a category will be counted once under the maximum severity and by causal relationship to study vaccine. Formal statistical testing comparing groups is not planned since interpretation of differences must rely heavily upon clinical judgement. Parallel analyses will include all AESIs, serious adverse events and adverse events leading to participant withdrawal or early discontinuation of study vaccine(s).

For this study events of interest are PIMMCs. PIMMCs that are recorded as MAAEs will be collected and analyzed.

Summaries, listings, datasets, or participant narratives may be provided, as appropriate, for those participants who die, who discontinue treatment due to an adverse event, or who experience a serious adverse event or an AESI.

Summaries and listings may be provided separately for adverse events with onset outside the above defined timeframe and that were reported pre-dose at the moment of subsequent vaccinations.

11.6.3. Other Safety Parameters

Vital Signs

The percentage of participants with values beyond pre-specified limits will be summarized.

Physical Examination

Physical examination findings will not be tabulated separately. Clinically relevant findings will be reported as adverse event and will be tabulated and listed as adverse events. BMI will be calculated using the recording of height at screening.

11.6.4. Other Parameters

Participant Reported Outcomes

Data from the social impact questionnaire, sexual activity questionnaire, the questionnaire on the use of PrEP and the level of absenteeism and vaccine regimen acceptance will be summarized using descriptive statistics:

1. In vaccine and placebo recipients,
2. In participants who become HIV-1 infected in comparison to non-infected participants,
3. In VISP positive and negative study participants,
4. In participants who are using PrEP or not during the course of the study, if applicable.

In addition, data may be included as co-variates in the exploratory efficacy analysis.

Health Economics Aspects (HCRU)

Health Care Resource Utilization will be described based on data collected through MAAEs and follow-up of HIV infections, and complemented by description of absenteeism.

1. Data will be summarized using descriptive statistics: In vaccine and placebo recipients,
2. In participants who become HIV-1 infected in comparison to non-infected participants,
3. In VISP positive and negative study participants,
4. In participants who are using PrEP or not during the course of the study, if applicable.

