The study comprises of a screening period of 45 days, a 12-month vaccination period and a follow-up period of at least 18 months after the fourth vaccination (until Month 30) in participants who remain HIV-1 negative or up to 6 months after diagnosis of HIV-1 infection in participants who become HIV-1 infected. Participants who completed their Month 30 visit will be followed for HIV infection, MAAEs and serious adverse events until the end of the study (ie, when the last participant completed the Month 30 visit or discontinued earlier). At the end of the study, participants may be offered the possibility to enter a long-term follow-up phase or program (to collect, amongst others, additional durability data).

After vaccination, participants will remain under observation at the study site for at least 30 minutes for presence of any acute reactions. In addition, participants will record solicited signs and symptoms in a diary for 7 days post-vaccination. Unsolicited adverse events will be recorded for all participants until 28 days after each preceding vaccination. From the time of local approval of protocol amendment 5 onwards, TTS is considered to be an AESI. Thrombotic events and/or thrombocytopenia (defined as platelet count below the lower limit of normal (LLN) range for the testing lab) are considered to be potential AESIs. All AESIs, including potential AESIs, will be reported to the sponsor from the moment of first vaccination until 6 months after the last vaccination. Each potential AESI will be reviewed to identify a TTS case. Serious adverse events, MAAEs, and adverse events leading to discontinuation will be collected for all participants until the end of the study. For details on reporting period of unsolicited adverse events, MAAEs, and serious adverse events, see Section 9.4. In addition, physical examinations, which includes vital sign measurements, and pregnancy testing will be performed.

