**NOTE:**

a The start time of screening phase is 00:00. In case an earlier date is available (e.g. for lab or vital signs then use the very first date in order to include all data)

b In case a dose is not administered, the observations end up in the previous Follow-Up phase

c For interim analyses a cut-off date will be identified: all data included in the analysis will go up to the cut-off date, any data referring to a later time point will not be included; ongoing events will be included and duration will be up to the cut-off date.

The periods/phases will be used primarily for safety. The post-dose periods (and the regimen phase) are considered active periods/phase, and the screening and follow-up phases are considered non-active phases for the evaluation of safety parameters. Efficacy endpoints will be calculated as described in Section 5.3.

For descriptive statistics over time, assessments (regardless of the investigated parameter) will be allocated to an analysis visit based on the visit number as captured in the database.

For participants who missed one or more doses but continued their planned visit schedule, the measurements after a planned but not administered dose will not be included in graphs and tables showing descriptive statistics over time. Those measurements will be shown in listings, but it will be indicated that these are not used in the analysis. Moreover, the vaccinations done after a missed vaccination will not be shifted to the previous vaccination but will be considered “as planned”: if for example the 2nd dose is missed, the 3rd dose vaccination will still be reported as post-dose 3.

Unless stated otherwise all analysis outputs will be shown by vaccine regimen (Vaccine vs Placebo).

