### **3.7. Health Economics Aspects (HCRU)**

Health Care Resource Utilization will be summarized based on data collected through MAAEs and follow-up of HIV infections, and complemented by description of absenteeism.

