### 4.1. Analysis of Adverse Events

Number and percentage of participants with at least one particular AE (unsolicited/solicited) will be tabulated. Unsolicited AEs will be summarized by System Organ Class and Preferred Term. Solicited AEs will be summarized by class (administration site, systemic) and preferred term.

For solicited AEs following tables will be provided: summary, by worst severity grade, grade 3 or above, related (systemic only), time to onset (in days) and duration (in days) for most frequent events and body temperature. Note: Duration is defined as number of days from the start of the event until resolution of the event. The time to first onset is defined as (date of first onset – reference date + 1). The reference date is the start date of the vaccination period.

For unsolicited AEs following tables will be provided: summary table (including SAE, fatal outcome, AESI and discontinuation), all events, most frequent, grade 3 or above, permanent stop of vaccine, related, SAE and AESI.

Listings and/or participant narratives will be provided as appropriate, for those participants who die, discontinue study vaccinations due to an AE, or experience a severe or serious AE.

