**4.3. Missing Data**

Missing data will not be imputed. Participants who do not report an event will be considered as participants without an event. An AE with a missing severity or relationship will be considered as an AE reported, but will be considered as not reported for the severity or relationship. For example, an AE with missing severity will be considered as an AE reported for the analysis of any grade, but will be considered as not reported for the analysis of grade 3 or above.

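### The infected versus non-infected comparison of MAAE-based resource use needs person-time split at HIV-1 diagnosis, because follow-up differs by design and most observed time in the infected group precedes infection

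*Protocol*

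**What the plan says.** Exploratory objective 7 (Protocol 2.1, Table 1) is to describe health care resource utilization (HCRU). Protocol 11.6.4 names the sources: "Health Care Resource Utilization will be described based on data collected through MAAEs and follow-up of HIV infections, and complemented by description of absenteeism". It then lists four groupings, one of which is "In participants who become HIV-1 infected in comparison to non-infected participants". No metric is given beyond descriptive statistics.

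Follow-up differs by infection status. Protocol 3.1 sets it at "up to 6 months after diagnosis of HIV-1 infection in participants who become HIV-1 infected", and Protocol 9.1.7 schedules two visits after the confirmatory visit, about 3 and 6 months from the first positive test. Under Protocol 10.1 the other participants continue until the last participant has had Month 30 or left.

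The statements on MAAE collection in infected participants differ. Footnote e of the Time and Events Schedule for infected participants ends collection at the last study contact. Protocol 9.1.7 says it runs to the end of the study for everyone.

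SAP 3.7 is one sentence: "Health Care Resource Utilization will be summarized based on data collected through MAAEs and follow-up of HIV infections, and complemented by description of absenteeism". It gives no infected/non-infected split, rate or denominator. By default (SAP 2.1.1, notes to Table 1) outputs are shown by vaccine group, and SAP 1 defers table layouts to the Data Presentation Specifications (DPS). The nearest stated event metric is in the safety section, SAP 4.1: "Number and percentage of participants with at least one particular AE (unsolicited/solicited) will be tabulated". SAP 4.3 adds: "Participants who do not report an event will be considered as participants without an event".

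**The concern.** The grouping classifies whole participants by something that happens part-way through follow-up. This has two separate effects.

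- **Shorter observation.** An infected participant's schedule ends about 6 months after diagnosis, so there is less time in which an MAAE can be recorded. A count or percentage per participant treats the unobserved months as event-free.
- **Misallocated time.** Everything before diagnosis, when the person was not known to be infected, is credited to the infected group. This dilutes any change after infection even if total observed time is used as the denominator.

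This grouping is the protocol's only contrast of resource use by infection status. A table built on it could suggest that HIV infection goes with no more medical visits, or fewer, only because observation stopped.

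**Working it through.** **1. Reproducing the plan's own figure.** Inputs from Protocol 11.3: 1,900 per arm, 5% excluded from per-protocol, 2% annual placebo incidence, 10% annual dropout, VE 20% to Month 7 and 65% after. With constant hazards h (infection) and m (dropout), expected infections per arm over Months 7 to 30 are

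1,805 × exp[−(h₀ + m) × 7/12] × h₁/(h₁ + m) × {1 − exp[−(h₁ + m) × 23/12]}.

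With m = 0.10, placebo (h₀ = h₁ = 0.02) gives 57.6 and vaccine (h₀ = 0.016, h₁ = 0.007) gives 20.5. The total is 78.1 against 78 stated. Power: |ln(0.35/0.80)| = 0.827; SE = √(1/57.6 + 1/20.5) = 0.257; 0.827/0.257 − 1.96 ≈ 1.25, hence 89.5% against about 90% stated. Both reproduce.

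**2. Observed time.** The same inputs, with 12-month accrual halved in the first 3 months, were simulated for 2,000,000 participants (dropout hazard −ln 0.9 = 0.105 per year). Diagnosis falls at the next scheduled visit. Infected participants are observed to the earliest of diagnosis + 6 months, dropout or study end; the others to dropout or study end. About 132 of 3,800 become infected.

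Let A be mean months before diagnosis and B after diagnosis in the infected, and U mean months in the non-infected.

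| Scenario | A | B | A + B | U | (A + B)/U | Break-even R |
|---|---|---|---|---|---|---|
| Base case | 16.6 | 5.4 | 22.0 | 30.2 | 0.73 | 2.51 |
| Counting stops at own Month 30 | 14.8 | 5.1 | 20.0 | 26.3 | 0.76 | 2.23 |
| VE = 0 | 17.4 | 5.4 | 22.9 | 30.2 | 0.76 | 2.36 |
| 5% dropout | 17.0 | 5.5 | 22.5 | 32.7 | 0.69 | 2.87 |
| 20% dropout | 15.6 | 5.3 | 20.9 | 25.7 | 0.81 | 1.89 |
| No dropout | 17.6 | 5.5 | 23.1 | 35.3 | 0.65 | 3.23 |

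(Sums and ratios were taken before rounding.) In the base case 16.6/22.0 = 75% of infected participants' observed time is before diagnosis.

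**3. What a comparison would show.** Assume one constant background MAAE rate for everyone, multiplied by R after diagnosis. The documents give no MAAE rate, but the ratios of mean counts and of rates do not depend on its level.

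- Mean count per participant, infected/non-infected = (A + R·B)/U. At R = 1: 22.0/30.2 = 0.73. At R = 2: 27.4/30.2 = 0.91. At R = 3: 32.8/30.2 = 1.09.
- Break-even R = (U − A)/B = (30.2 − 16.6)/5.4 ≈ 2.5. Below this, a count shows no excess or a deficit.
- Rate over whole follow-up = (A + R·B)/(A + B). At R = 2: 27.4/22.0 = 1.25.
- Rate with time split at diagnosis: R itself, 2.0 when R = 2.

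If instead the rate were higher throughout in those who become infected, a count would show an excess only beyond 30.2/22.0 = 1.37.

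**4. Percentage with at least one MAAE.** This does depend on the background rate. At an assumed 1 per year, base case, R = 1.5 gives 83.2% infected versus 86.6% non-infected (reversed), and R = 2 gives 86.7% versus 86.6% (hidden). At 2 per year, R = 2 gives 97.3% versus 94.6%, so an excess is visible. With 20% dropout and 1 per year, R = 1.5 gives 81.6% versus 79.1%, also visible.

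**The case against.** The strongest reply is that the metric is being supplied by the reader. Protocol 11.6.4 promises only descriptive statistics, SAP 3.7 only a summary, and the layouts sit in the DPS. SAP 4.1 and 4.3 are safety rules that are not applied to HCRU. This stands: understatement cannot be called certain. It does not remove the point, because the grouping is fixed and misleads under either natural metric (0.91 on counts, 1.25 on whole-follow-up rates, for a true 2.0).

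A reader might also infer the following, which the documents do not support:

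- **That the SAP plans this comparison.** SAP 3.7 has no such split and the default is by vaccine group. The protocol comparison is simply not carried forward.
- **That the direction always reverses.** At a true ratio of 3 the base-case count ratio is 1.09: attenuated, not reversed.
- **That absenteeism shrinks in the same way.** It is asked at each visit for the interval since it was last recorded (Protocol 9.5.4), so a by-visit summary would not fall with shorter follow-up. The documents do not say whether it is summed. Mixing of pre- and post-diagnosis intervals remains possible.
- **That the whole HIV burden rests on MAAEs.** Follow-up of HIV infections is a stated second source. Confirmed HIV-1 infection is not itself recorded as an adverse event (Protocol 9.2).
- **That the PrEP-use grouping in the same list has the same defect and remedy.** No calculation here covers it, and a split at HIV diagnosis does not define time on PrEP.

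It is also fair that 9.1.7 extends MAAE recording to the end of the study. But the infected schedule has no visit after the 6-month one at which to collect them.

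**Conclusion.** The point holds in limited form. The protocol's infected/non-infected grouping of MAAE-based resource use compares about 22 with about 30 months of observation (ratio 0.73; 0.65 to 0.81), with about three quarters of the infected time before diagnosis. On per-participant counts, an increase after infection is attenuated, and it is hidden or reversed unless the true post-diagnosis ratio exceeds about 2.5 (1.9 to 3.2). On percentages the result varies with the background rate. Rates over whole follow-up avoid the observation-time effect but still dilute a doubling to 1.25.

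These sizes rest on the plan's design assumptions, on MAAE collection stopping at about 6 months after diagnosis, and on an assumed common background rate that changes only at diagnosis. The SAP's amendment history records unblinding for non-efficacy in January 2023, so realised follow-up may differ; the VE = 0 scenario gives 0.76. Only exploratory objective 7 is affected. The primary efficacy analysis is not.

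**What to change.** 1. In Protocol 11.6.4, and by adding the comparison to SAP 3.7 and the DPS, report MAAEs per person-time of actual observation, split at the date of HIV-1 diagnosis. Time before diagnosis counts as uninfected; time from diagnosis to last contact counts as infected.
2. For absenteeism, report days absent over days since the previous recording, by visit interval, with intervals before and after diagnosis shown separately.
3. Reconcile footnote e of the infected-participant schedule (MAAEs to last study contact) with Protocol 9.1.7 (to end of study), so that the end of the observation period is defined.

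The cost is wording and a denominator from dates already collected; no new data are needed. The downside is precision: with about 5.4 months per infected participant after diagnosis, the infected rates will have wide intervals.
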